10.2.1. Within-treatment Changes

For variables measured on a continuous scale, the statistical significance of each parameter will be investigated using a paired t-test.

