7. SUBJECTS

7.1. Subject Population

Eligible test subjects will be 21 to 39 years of age or older and who are interested in and appropriate candidates for LASIK.

A total of 104 eyes of 52 subjects at one site will be enrolled. Both eyes of a subject must be enrolled. Subjects must meet the inclusion criteria. Prior to enrollment, subjects will be provided information on the study and asked to sign a patient information and consent form to participate. The patient information and consent form will be approved by an appropriate ethics committee.

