8. STUDY DESIGN

8.1. Study Design

This study is a single site, single-arm, prospective, observational study of subject satisfaction, after successful bilateral LASIK surgery. Subjects will be assessed pre-operatively, operatively and at 1 week, 1 month, and 3 months post-operatively. Clinical evaluations will include measurement of visual acuity, manifest refraction, and topography, aberrometry, and administration of the OSDI and PROWL questionnaires.

The primary outcome measure will be the percentage of subjects satisfied (Completely Satisfied or Very Satisfied) with vision after Phorcides Planned Contoura LASIK based on PROWL Questionnaire preoperative vs postoperative (question #1 only).

Secondary outcome measures are as follows:

• Percentage of eyes with post-op spherical equivalent within +/- 0.50 D.

Exploratory outcome measures are as follows:

- Preoperative and postoperative higher order aberrations (spherical aberration and coma).
- Preoperative and postoperative responses on the PROWL questionnaire (Q2-Q33).
- Preoperative and postoperative OSDI scores.
- Correlation of postoperative OSDI score and responses on the postoperative PROWL questionnaire (Q1).

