9.2.2. Operative (Surgery)

All subjects will undergo bilateral LASIK surgery. The surgeon's usual standard of care with regard to treatment and medication will be used for all study subjects. Surgery planning will be performed using the surgeon's preferred method.

Any adverse events/serious adverse events (AEs/ SAEs) occurring during surgery will be noted at this visit. Any other problems during surgery and comments regarding surgery will be documented.

Any subject whose surgery is not completed successfully will be documented in the appropriate case report form. These subjects will be monitored for safety but clinical performance data may be excluded from the analysis.

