10. ANALYSIS PLAN

10.1. Analysis Data Sets

All subjects who are enrolled in the study will be evaluated for safety. Efficacy analyses will be performed based on data from those eyes with uncomplicated LASIK surgery.

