10.2. Statistical Methodology

A summary of the data will be prepared for all measurement time points.

For variables measured on a continuous scale, these summaries will include the sample size, as well as the mean, standard deviation, median, minimum, and maximum. For variables measured on a categorical scale, summaries will provide the number and percentage of subjects in each category. These summaries will be provided for all eyes completing the study.

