10.3. General Statistical Considerations

The statistical analyses will be performed using R, version 4.1.2 or higher. Any statistical tests of hypotheses will employ a level of significance of alpha=0.05.

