11. SAMPLE SIZE JUSTIFICATION

We estimate that the study would require a sample size of 46 subjects (number of pairs) to achieve a power of 90% and a level of significance of 5%, for detecting a mean of difference of 25 points in satisfaction (using the PROWL questionnaire) between pairs, and assuming the standard deviation of the differences to be 50 points.³ To account for dropout, 52 subjects will be enrolled.

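### The paired t-test has no stated unit and the plan does not handle fellow eyes; run on the eye-level efficacy set, its error rate for per-eye continuous variables is not 5% unless fellow-eye changes are uncorrelated

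*Combined protocol and SAP*

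**What the plan says.** Section 10.2.1 is the whole inferential plan for continuous variables: "For variables measured on a continuous scale, the statistical significance of each parameter will be investigated using a paired t-test". Section 10.3 adds the level: "Any statistical tests of hypotheses will employ a level of significance of alpha=0.05". Neither names the unit of the test.

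The neighbouring sections do not settle it:

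- Towards eyes: section 10.1 states "Efficacy analyses will be performed based on data from those eyes with uncomplicated LASIK surgery", and section 10.2 closes with "These summaries will be provided for all eyes completing the study".
- Towards subjects: section 10.2 also counts subjects, not eyes, when it describes categorical summaries. Section 11 refers to "a sample size of 46 subjects (number of pairs"), but only for PROWL satisfaction, which has one value per subject.
- Neutral: section 9.2.2 says of subjects whose surgery was not completed successfully, "These subjects will be monitored for safety but clinical performance data may be excluded from the analysis". That is a discretionary exclusion and does not define a unit.

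Section 7.1 requires two eyes from everyone ("Both eyes of a subject must be enrolled"), which gives 104 eyes of 52 subjects. Table 15.1 has both eyes tested, with aberrometry before surgery and at 3 months. Section 8.1 lists among the exploratory outcomes "Preoperative and postoperative higher order aberrations (spherical aberration and coma"). No section mentions averaging of eyes, selection of one eye, a mixed model or any other handling of fellow eyes.

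**The concern.** A paired t-test on eyes removes the correlation between the two time points within one eye. It does nothing about the correlation between the two eyes of one person. An analyst who applies section 10.2.1 to the data set of section 10.1 would enter up to 104 differences as if they came from 104 people. If fellow-eye changes are positively correlated, the standard error is too small and so are the p-values, and a chance change in an aberration could be reported as significant.

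With the unit left open, two analysts could also obtain different p-values from the same data, and the choice could be made after seeing them.

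The reach is limited to continuous variables with one value per eye. These are spherical aberration and coma, and refraction and acuity to the extent that the wording of 10.2.1 is taken to cover them.

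**Working it through.** **The plan's own figure.** Section 11 gives 46 subjects for 90% power at 5%, with a mean difference of 25 and an SD of differences of 50. On a two-sided reading, n = ((1.960 + 1.282) × 50/25)² = 42.03, so 43 by the normal approximation. The exact paired t-test needs 44 (power 0.900), and 46 gives power 0.913. The stated 46 is reproduced to within two subjects. It is a subject-level calculation, so the question of eyes does not touch it.

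**Inputs for the eye-level test.** 52 subjects with two eyes each (section 7.1) and alpha 0.05 (section 10.3), taken as two-sided because sidedness is not stated. The correlation ρ between the pre-to-post changes of fellow eyes is not in the documents. It is assumed over a range that includes negative values.

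**Formulas.** With two eyes per subject the variance of the mean change is (1 + ρ) times the value the eye-level test uses, so:

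- true SE / SE used = √(1 + ρ)
- true type I error ≈ 2 × (1 − Φ(1.96/√(1 + ρ)))
- subject-level p matching an eye-level p of 0.05: divide the critical t on 103 df (1.983) by √(1 + ρ) and refer the result to t on 51 df, with variances at their expected values.

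Example at ρ = 0.5: √1.5 = 1.225; 1.96/1.225 = 1.600; type I error = 0.110. For the p-value, 1.983/1.225 = 1.619, which on 51 df gives 0.11.

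| Assumed ρ | Type I error, eye-level test (formula) | Same, simulated, 104 eyes | Subject-level p when eye-level p = 0.05 |
|---|---|---|---|
| −0.3 | 0.019 | 0.019 | 0.022 |
| −0.1 | 0.039 | 0.039 | 0.042 |
| 0 | 0.050 | 0.049 | 0.053 |
| 0.1 | 0.062 | 0.062 | 0.064 |
| 0.3 | 0.086 | 0.086 | 0.088 |
| 0.5 | 0.110 | 0.110 | 0.11 |
| 0.7 | 0.133 | 0.134 | 0.13 |
| 0.9 | 0.155 | 0.157 | 0.16 |

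The simulation used normally distributed changes and 200,000 runs per setting. With 92 eyes (46 subjects) the results agree to within 0.2 percentage points. If 4 of the 52 subjects contribute one eye (an assumption), the error rates are slightly lower: 0.060 at ρ = 0.1 and 0.154 at ρ = 0.9.

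**Check of the remedy.** On the same simulated data, a t-test on the per-subject mean of the available eyes rejects in 4.9% to 5.0% of runs in every setting. A random-intercept model with its variance held at zero or above was also simulated (52 subjects, 51 df, 100,000 runs). It rejects in 4.1% of runs at ρ = 0, 3.4% at −0.1 and 1.9% at −0.3, so it is conservative there.

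**The case against.** The strongest reply is that this is an omission and not a stated error. Section 10.1 says whose data enter the efficacy analyses; it does not name the unit of a test. It cannot set the unit throughout, because the primary outcome is a percentage of subjects. Section 10.2 mixes eyes and subjects, and the only place that defines a pair, section 11, counts subjects. Harm also requires that fellow-eye changes are positively correlated and that an exploratory result lies close to 0.05. The documents establish neither.

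Most of this stands. It makes the error conditional and keeps the consequence modest. It does not supply the missing unit: section 11 concerns a questionnaire score with one value per person and is silent on variables with two. Exploratory status lowers the stakes but does not make the standard error right.

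A reader might infer that the plan commits to pooling eyes. It does not say so. A reader might also infer that the p-values must come out too small. That needs a positive correlation, which is plausible but assumed. The documents do not even say whether coma is analysed as a magnitude or as signed components, and at negative correlation the eye-level test is conservative.

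**Conclusion.** The point holds in conditional form. Confidence is high that the unit and the handling of fellow eyes are missing, and moderate that the test would be run on eyes.

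If it is, the nominal 5% level is right only at zero correlation. The actual level is about 6% to 16% for ρ from 0.1 to 0.9, and falls to 1.9% at ρ = −0.3. The whole range rests on an assumed ρ.

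It would be wrong to read this as a threat to the study's main result. PROWL question 1 and OSDI have one value per subject, the sample size is by subject, and the secondary percentage of eyes within ±0.50 D is unaffected as a point estimate. The change should be made, but the study's objective does not depend on it.

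**What to change.** In section 10.2.1, state that for continuous variables measured per eye the change from before surgery to 3 months is averaged over the subject's available eligible eyes, and that the paired t-test is run with the subject as the unit. This holds the level whatever the sign of the correlation, and also when some subjects contribute one eye.

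A mixed model with a subject random intercept may be added as a sensitivity analysis, with a note that it is conservative at zero or negative correlation when its variance is held at zero or above.

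The cost is one or two sentences and standard R functions. The effect on p-values depends on the correlation, as in the last column of the table: larger if it is positive, nearly unchanged at zero, smaller if it is negative.

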10.3. General Statistical Considerations

The statistical analyses will be performed using R, version 4.1.2 or higher. Any statistical tests of hypotheses will employ a level of significance of alpha=0.05.

11. SAMPLE SIZE JUSTIFICATION

We estimate that the study would require a sample size of 46 subjects (number of pairs) to achieve a power of 90% and a level of significance of 5%, for detecting a mean of difference of 25 points in satisfaction (using the PROWL questionnaire) between pairs, and assuming the standard deviation of the differences to be 50 points.³ To account for dropout, 52 subjects will be enrolled.

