3. GENERAL INFORMATION

Objective	To determine the percentage of subjects satisfied (Completely Satisfied or Very Satisfied) with vision after Phorcides Planned Contoura LASIK. The hypothesis is that a high percentage of subjects receiving the Phorcides Planned Contoura LASIK will be satisfied with their vision		
	Phorcides Planned Contoura LASIK will be satisfied with their vision.		
Test Article(s)	WaveLight® EX500 Contoura laser		
Control Article(s)	None.		
Sample size	104 eyes of 52 subjects		
Study Population	Subjects 21 to 39 years of who are appropriate candidates for laser refractive surgery.		
Number of sites	One		
Study Design	Single site, single-arm, prospective, observational study		
Masking	None		
Variables	Primary: Percentage of subjects satisfied (Completely Satisfied or Very Satisfied) with vision after Phorcides Planned Contoura LASIK based on PROWL Questionnaire preoperative vs postoperative (question #1 only).		
	Secondary:		
	• Percentage of eyes with post-op spherical equivalent within +/- 0.50 D.		
	 Exploratory: Preoperative and postoperative higher order aberrations (spherical aberration and coma). Preoperative and postoperative responses on the PROWL questionnaire (Q2-Q33). Preoperative and postoperative OSDI scores. Correlation of postoperative OSDI score and responses on the postoperative PROWL questionnaire (Q1). 		
Duration / Follow-up	Preoperative to 3 months postoperative		

The study will be registered with clinicaltrials.gov.

The study will be conducted in compliance with the protocol, GCP and applicable regulatory requirements

4	TARLE	OF	CONTENTS
H .	IADLL	UF	CONTENTS

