6. OBJECTIVE(S)

To determine the percentage of subjects satisfied (Completely Satisfied or Very Satisfied) with vision after Phoreides Planned Contoura LASIK.

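### The primary endpoint is a percentage satisfied, but the plan gives it no confidence interval or test, and the 90% power is stated for a mean difference in points

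*Combined protocol and SAP*

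**What the plan says.** - **Objective (Section 6):** "To determine the percentage of subjects satisfied (Completely Satisfied or Very Satisfied) with vision after Phoreides Planned Contoura LASIK".
- **Primary outcome (Section 8.1):** "The primary outcome measure will be the percentage of subjects satisfied (Completely Satisfied or Very Satisfied) with vision after Phorcides Planned Contoura LASIK". It is based on "PROWL Questionnaire preoperative vs postoperative (question #1 only"). Section 3 describes the primary variable the same way.
- **Hypothesis (Section 3):** "The hypothesis is that a high percentage of subjects receiving the Phorcides Planned Contoura LASIK will be satisfied with their vision". No threshold or null value is given.
- **Categorical data (Section 10.2):** "For variables measured on a categorical scale, summaries will provide the number and percentage of subjects in each category".
- **The only named test (Section 10.2.1):** "For variables measured on a continuous scale, the statistical significance of each parameter will be investigated using a paired t-test".
- **Significance level (Section 10.3):** "Any statistical tests of hypotheses will employ a level of significance of alpha=0.05". No test is assigned to the primary.
- **Sample size (Section 11):** 46 pairs for 90% power at the 5% level, for "detecting a mean of difference of 25 points in satisfaction (using the PROWL questionnaire) between pairs", with an SD of the differences of 50 points. Enrolment is raised to 52 for dropout.

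**The concern.** There are two gaps.

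**Analysis.** The primary variable is a yes/no classification of each subject, so the categorical rule in Section 10.2 governs it. That rule yields a point estimate and nothing else. The before-versus-after comparison in Sections 3 and 8.1 has no method, and no benchmark says what a high percentage would be.

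**Sample size.** Section 11 powers a mean difference on a points scale that the documents do not define for question 1. It gives no rate of subjects gaining or losing satisfied status and no share of discordant pairs, and these determine the power of a paired comparison of percentages.

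At stake are the uncertainty attached to the headline percentage and the meaning of the 90%, which a reader would naturally take to apply to the primary endpoint. With no method named, the choice among a bare percentage, an exact or asymptotic McNemar test, or a t-test on scored responses stays open until the data are seen. The study is single-arm and unmasked, so pre-specification is one of its few safeguards.

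**Working it through.** **1. Reproducing the 46 pairs.** Inputs from Section 11: difference 25, SD 50, power 90%, alpha 5%. Sidedness is not stated; two-sided is assumed.

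- Normal approximation: n = ((1.960 + 1.282) × 50/25)² = 42.03, so 43.
- Noncentral t with effect size 25/50 = 0.5: 44 pairs give power 0.900, 46 give 0.913 and 52 give 0.943.
- One-sided, 36 pairs would be enough, so two-sided is the better match to 46.
- Dropout: 1 − 46/52 = 11.5%. The plan states no rate.

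The figure of 46 is sound for a mean paired difference.

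**2. Moving to the binary primary.** Code each subject 0 or 100 for not satisfied or satisfied, and take post minus pre. On the 0–1 scale let p10 be the share who gain satisfied status, p01 the share who lose it, and pd = p10 + p01 the discordant share. Then

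- mean difference = p10 − p01
- SD² = pd − (p10 − p01)²

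With mean 0.25 and SD 0.50, pd = 0.25 + 0.0625 = 0.3125, so p10 = 0.28125 and p01 = 0.03125. This is the only discordant share consistent with Section 11 under that coding. The documents do not state the coding.

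**3. McNemar power.** Power = Σ over m of Bin(m; n, pd) × P(reject given m discordant pairs), where gains among the m are binomial with probability p10/pd. The exact test rejects when the two-sided binomial p-value is at most 0.05. The asymptotic test (no continuity correction) rejects when (2x − m)²/m ≥ 1.96², x being the number of gains. The net gain is 25 percentage points throughout, and the last column is the 95% Wald half-width for the paired difference, 1.96 × SD/√46.

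| Discordant share | Implied SD (points) | Exact, n = 46 | Asymptotic, n = 46 | Exact, n = 52 | Half-width, n = 46 (points) |
|---|---|---|---|---|---|
| 25% | 43 | 98.5% | 99.9% | 99.5% | ±12.5 |
| 31.25% | 50 | 87.6% | 92.0% | 92.0% | ±14.4 |
| 40% | 58 | 74% | 81% | 80% | ±16.8 |
| 50% | 66 | 61% | 71% | 68% | ±19.1 |

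Only the 31.25% row agrees with the stated SD of 50. The other rows are assumed sensitivity cases. At 31.25% discordant, the exact test needs 49 pairs for 90% power.

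**4. Precision of the postoperative percentage at n = 46 (Clopper–Pearson 95%).**

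- 37/46 (80%): 66.1% to 90.6%
- 41/46 (89%): 76.4% to 96.4%
- 44/46 (96%): 85.2% to 99.5%

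The expected width is 18.9 points at a true 90% and 24.4 points at a true 80%. An interval of that size affects whether an observed percentage can be called high.

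**The case against.** The best defence is that points means percentage points. Under that reading Section 11's two numbers fix the gain, loss and discordant shares, and power is 87.6% (exact) or 92.0% (asymptotic) at 46 pairs, or 92.0% and 95.0% if all 52 are evaluable. The 90% would then be about right. This stands as a possible reading and rules out calling the study underpowered. It does not close the gap, because Section 11 states neither the coding nor a test for proportions. The lower power figures also depart from the plan's SD of 50, and the documents offer no basis for 40% or 50% discordance; they show sensitivity, not a deficit.

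Second, the scale may be defined in the published study that Section 11 cites. That source is not among the documents, so the claim is only that they do not define it. One sentence could settle this.

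Third, this is a single-arm observational study that sets out to determine a percentage, and a count and percentage do that. A benchmark for high would add a confirmatory aim the sponsor may not want. That is fair, and the benchmark is optional. But the plan also states a hypothesis, a before-versus-after comparison, an alpha and a power. Even a purely descriptive aim needs a stated precision.

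Finally, an interval and a McNemar result could be computed later from the same data. They could, but they would not be prespecified.

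**Conclusion.** The concern holds. As written, the primary percentage has no confidence interval and no test, its before-versus-after comparison has no method, and the 90% power belongs to a mean difference on an undefined scale. The sample-size arithmetic is correct for that mean.

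For the binary primary, power is not established. It is near 90% under one unstated coding, and the exact-test figure runs from 98.5% down to 61% for the same 25-point gain as the discordant share goes from 25% to 50%. These figures assume two-sided 5% tests and 46 evaluable pairs. With 46 subjects, an observed percentage near 90% would carry an interval about 20 points wide that the plan does not call for.

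This should be fixed. The point estimate survives, but its uncertainty, the inference on change and the meaning of the power statement do not.

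**What to change.** **Section 10.2.** Name the primary analysis:

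- the percentage of subjects in the top two categories of question 1 at Visit 5, with an exact (Clopper–Pearson) 95% confidence interval;
- the preoperative-to-Visit 5 comparison by a McNemar test, stated as exact or asymptotic and two-sided at 5%, with the paired difference in percentages and its 95% confidence interval.

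If a numeric question 1 score is also wanted, define it and list its paired t-test as supportive.

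**Section 11.** State that the 90% refers to a mean score difference, and define the score behind the points. Replace or supplement it with power for the binary primary under assumed and justified gain and loss rates, over a range of discordance. Add the expected interval width at 46 evaluable subjects. If points means percentage points on a 0/100 indicator, say so and give the implied 28.1% gain and 3.1% loss.

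**Section 3.** Recast the hypothesis as estimation or, if a claim of high satisfaction is intended, set in advance a benchmark for the lower confidence limit.

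**Cost.** Wording in three sections. Enrolment stays at 52, with no extra visits or data. The stated power becomes conditional on assumed rates and may look slightly less favourable, for example 87.6% with the exact test at 46 pairs.

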13. QUALITY COMPLAINTS AND ADVERSE EVENTS

All subjects will be monitored for adverse events over the course of the study. A place to record any adverse event is included on each case report form.

13.1. General Information

An Adverse Event (AE) is any untoward medical occurrence in a subject who is administered. a study treatment regardless of whether or not the event has a causal relationship with the treatment. An AE, therefore, can be any unfavorable or unintended sign (including an abnormal laboratory finding), symptom, or disease temporally associated with the study treatment, whether or not related to the treatment. In clinical studies, an AE can include an untoward medical occurrence occurring at any time, including run-in or washout periods, even if no study treatment has been administered.

